#### 4.6.1 Safety Oversight by the Dose Escalation Steering Committee

A DESC comprised of ADC Therapeutics and the investigators will review patient safety on an ongoing basis during Part 1 to determine if the dose escalation schedule prescribed by the mCRM warrants modification. In addition to safety observations, PK and/or PD data may also inform DESC decision making. Intermediate doses or extended dosing intervals may be assigned after agreement between ADC Therapeutics and the investigators. The DESC will continue to provide oversight during Part 2. No formal Data Safety Monitoring Board (DSMB) will be used.

#### 4.6.2 Definition of Dose-Limiting Toxicities

A DLT is defined as any of the following events that occur during the 21-day DLT evaluation period, except those that are clearly due to underlying disease or extraneous causes.

A hematologic DLT is defined as:

Event	Severity
Febrile neutropenia or neutropenic infection	Grade 3 or 4
Neutropenia lasting > 7 days	Grade 4
Thrombocytopenia	Grade 4
Thrombocytopenia with clinically significant bleeding	Grade 3
Thrombocytopenia requiring a platelet transfusion	Grade 3
Anemia	Grade 4
Anemia requiring transfusion	Grade 3

A non-hematologic DLT is defined as:

Event	Severity
Hy's law case	AST and/or ALT > 3x ULN and bilirubin > 2x ULN, and without initial findings of cholestasis (serum alkaline phosphatase (ALP) activity < 2x ULN) and no other reason that could explain the combination of increased transaminases and serum total bilirubin, such as viral hepatitis A, B, or C, preexisting or acute liver disease, or another drug capable of causing the observed injury.
Hypersensitivity/infusion-related	Grade 3 or higher. A Grade 3 hypersensitivity /

reaction (regardless of premedication)	infusion-related reaction that resolves within 24 hours after onset with appropriate clinical management does not qualify as a DLT.
All other non-hematologic toxicity	Grade 3 & 4

The following conditions are not considered non-hematologic DLTs:

Event	Severity
Fatigue	Grade 3 for $\leq$ 7 days.
Diarrhea, nausea, or vomiting	Grade 3 in the absence of premedication that responds to therapy and improves by at least 1 grade within 3 days for Grade 3 events or to $\leq$ Grade 1 within 7 days.
Serum lipase or serum amylase	Grade 3 for $\leq$ 7 days if without clinical signs or symptoms of pancreatitis.
Electrolyte abnormalities	$\leq$ Grade 3 which normalize within 48 hrs (with or without medical intervention) and which do not manifest themselves clinically; in such instance, a follow-up sample MUST be taken within 48 hrs to check whether such normalization has occurred.

Patients who experience a DLT that resolves or stabilizes with appropriate medical management may continue treatment at the discretion of the Investigator in consultation with the Sponsor.

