## 5 Management of Toxicity Including Dose Delays and Modifications

The Investigator may suspend ADCT-502 dosing for up to 1 cycle (i.e., 21 days of the default dosing schedule) for any patient who experiences a protocol-defined DLT. At the discretion of the Investigator, the dose may also be delayed for up to 21 days for any other toxicity of any grade.

Resumption of dosing with ADCT-502 after any suspension, even when longer than 21 days, is at the discretion of the Investigator, in consultation with the Sponsor, on assessment of the patient's clinical condition and whether or not the patient is deriving potential clinical benefit from treatment with ADCT-502.

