## 5.1 ADCT-502 General Dose Modification Guidelines

Guidelines for management of specific toxicities are detailed in [Sections 5.2, 5.3, and 5.4](#). For management of events not specified in these sections, the following may serve as a guidance to investigators:

AE Grade	ADCT-502 Management Guideline
1	No dose adjustment is required.
2	
First Occurrence:
 
Consider holding ADCT-502 until improvement to <math>\leq</math> Grade 1 or Baseline. Up to 1 dose of ADCT-502 may be skipped to permit improvement. If improvement to <math>\leq</math> Grade 1 or Baseline occurs within 21 days from the last scheduled (but missed) ADCT-502 dose, continue ADCT-502 at the original assigned dose level in subsequent treatment cycles.
 
If improvement to <math>\leq</math> Grade 1 or Baseline does not occur within 21 days from the last scheduled (but missed) ADCT-502 dose, permanently discontinue ADCT-502.
 
Second Occurrence:
 
Hold ADCT-502 until improvement to <math>\leq</math> Grade 1 or Baseline. Up to 1 dose of ADCT-502 may be skipped to permit resolution. If improvement to <math>\leq</math> Grade 1 or Baseline occurs within 21 days from the last scheduled (but missed) ADCT-502 dose, continue ADCT-502 at 1 dose level below the original assigned dose in subsequent treatment cycles. If improvement to <math>\leq</math> Grade 1 or Baseline does not occur within 21 days from the last scheduled (but missed) ADCT-502 dose, permanently discontinue ADCT-502.
 
Third Occurrence:
 
Permanently discontinue ADCT-502.

3	
First Occurrence:
 
Hold ADCT-502 until improvement to <math>\leq</math> Grade 1 or Baseline. Up to 1 dose of ADCT-502 may be skipped to permit improvement, then continue ADCT-502 at 1 dose level below the original assigned dose in subsequent treatment cycles.
 
Second Occurrence:
 
Permanently discontinue ADCT-502.

4	Permanently discontinue ADCT-502.

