## 5.2 Guidelines for Dose Modification: Hematologic Toxicities

Adverse Event	Grade	ADCT-502 Management Guideline
Febrile neutropenia	3	Hold ADCT-502 until the patient recovers. Up to 1 dose of ADCT-502 may be skipped to permit improvement. Consider use of granulocyte colony stimulating factor (G-CSF) as per institutional guidelines or as per ASCO guidelines. G-CSF prior to ADCT-502 is not allowed unless approved by sponsor.

Adverse Event	Grade	ADCT-502 Management Guideline
		
First Occurrence:
 
If patient recovers from febrile neutropenia prior to next scheduled dose or within 21 days from last scheduled (but missed) ADCT-502 dose, then continue ADCT-502 at 1 dose level below the original assigned dose in subsequent treatment cycles. If the patient does not recover within 21 days from the last scheduled (but missed) ADCT-502 dose, permanently discontinue ADCT-502.
 
Second Occurrence:
 
Permanently discontinue ADCT-502 if febrile neutropenia recurs despite ADCT-502 dose reduction.

Febrile neutropenia	4	Permanently discontinue ADCT-502.
Thrombocytopenia with significant bleeding or platelet transfusion required as per PI assessment	3	
Hold ADCT-502 until bleeding has stopped and improvement has occurred to <math>\leq</math> Grade 1. Up to 1 dose of ADCT-502 may be skipped to permit improvement.
 
First Occurrence:
 
Upon improvement to <math>\leq</math> Grade 1 within 21 days from last scheduled (but missed) ADCT-502 dose, continue ADCT-502 at 1 dose level below the original assigned dose in subsequent treatment cycles.
 
If improvement to CTCAE <math>\leq</math> Grade 1 does not occur within 21 days from the last scheduled (but missed) ADCT-502 dose, permanently discontinue ADCT-502.
 
Second Occurrence:
 
Upon improvement to <math>\leq</math> Grade 1 within 21 days from last scheduled (but missed) ADCT-502 dose, continue ADCT-502 at 2 dose levels below the original assigned dose in subsequent treatment cycles.
 
If improvement to <math>\leq</math> Grade 1 does not occur within 21 days from the last scheduled (but missed) ADCT-502 dose, permanently discontinue ADCT-502.
 
Third Occurrence:
 
Permanently discontinue ADCT-502.

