### 5.3 Guidelines for Dose Modification: Non-hematologic Toxicities

Adverse Event	Grade	ADCT-502 Management Guideline
Infusion-related reactions	1	
The infusion rate may be decreased by 50% or temporarily interrupted for up to 6 hours to permit resolution of the event.
 
Acetaminophen (paracetamol) and/or H1- and H2-receptor antagonists (e.g., diphenhydramine, ranitidine) may be administered for symptomatic treatment per institutional standard at the discretion of the Investigator.
 
Consider premedication (e.g., secondary prophylaxis) with acetaminophen (paracetamol) and/or H1- and H2-receptor antagonists at least 30 minutes prior to start of subsequent doses.

	2	
Interrupt ADCT-502 infusion for up to 6 hours to permit resolution of the event. If the event resolves within 6 hours, resume ADCT-502 infusion at 50% of the prior infusion rate. Acetaminophen (paracetamol) and H1- and H2-receptor antagonists (diphenhydramine and ranitidine) should be administered for symptomatic treatment. If the patient experiences chest tightness, dyspnea, or shortness of breath, IV methylprednisolone 100 mg (or the equivalent) should be administered.
 
If the event resolves within 6 hours and requires IV steroid treatment, pre-medicate (e.g., secondary prophylaxis) with acetaminophen (paracetamol), H1- and H2-receptor antagonists (e.g., IV diphenhydramine, and IV ranitidine), and IV methylprednisolone 100 mg (or the equivalent) at least 30 minutes prior to start of subsequent doses.
 
If the event resolves within 6 hours and did not require IV steroid treatment, pre-medication (e.g., secondary prophylaxis), at least 30 minutes prior to start of subsequent doses may be considered.

Adverse Event	Grade	ADCT-502 Management Guideline
Hypersensitivity and infusion-related reactions	3	Permanently discontinue ADCT-502 unless AE resolves within 24 hours after onset (with or without clinical management). Manage severe infusion-related reactions per institutional guidelines (i.e., treatment with IV diphenhydramine, IV ranitidine, and IV glucocorticoids).  Intramuscular epinephrine should be used after failure of other therapeutic options.
Hypersensitivity and infusion-related reactions	4	Permanently discontinue ADCT-502.
Transaminase (AST/ALT) Abnormalities	2	No dose modification is required.

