	3	Hold ADCT-502 until improvement to $\leq$ Grade 1 or Baseline. Up to 1 dose of ADCT-502 may be skipped to permit improvement.  First Occurrence:  If improvement to $\leq$ Grade 1 or Baseline occurs prior to next scheduled dose, continue ADCT-502 at the original assigned dose at the next scheduled treatment cycle.  If improvement to $\leq$ Grade 1 or Baseline within 21 days from last scheduled (but missed) ADCT-502 dose, continue ADCT-502 at 1 dose level below the original assigned dose in subsequent treatment cycles. If improvement to $\leq$ Grade 1 or Baseline does not occur within 21 days from the last scheduled (but missed) ADCT-502 dose, permanently discontinue ADCT-502.  Second Occurrence:  If improvement to $\leq$ Grade 1 or Baseline within 21 days from last scheduled (but missed) ADCT-502 dose, then continue ADCT-502 at 2 dose level below the original assigned dose in subsequent treatment cycles. If improvement to $\leq$ Grade 1 or Baseline does not occur within 21 days from the last scheduled (but missed) ADCT-502 dose, permanently discontinue ADCT-502.  Third Occurrence:  Permanently discontinue ADCT-502.
Hyperbilirubinemia	2	Hold ADCT-502 until improvement to $\leq$ Grade 1 or Baseline. If improvement to $\leq$ Grade 1 or Baseline occurs prior to next scheduled dose, continue ADCT-502 at the original assigned dose at the next scheduled treatment cycle.  First Occurrence:  If improvement to $\leq$ Grade 1 or Baseline within 21 days from last scheduled (but missed) ADCT-502 dose, continue ADCT-502 at 1 dose

Adverse Event	Grade	ADCT-502 Management Guideline
		
level below the original assigned dose in subsequent treatment cycles. If improvement to <math>\leq</math> Grade 1 or Baseline does not occur within 21 days from the last scheduled (but missed) ADCT-502 dose, permanently discontinue ADCT-502.
 
Consider close monitoring as needed.
 
Second occurrence:
 
Permanently discontinue ADCT-502
 
Permanently discontinue ADCT-502 for any case meeting Hy's Law criteria.

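### Section 4.6.2 lets dosing continue after any DLT that settles, Sections 5.2–5.3 order a permanent stop for three kinds of DLT, and no text says which governs

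*Protocol*

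**What the plan says.** **The permission.** Protocol Section 4.6.2 closes its DLT tables with this sentence: "Patients who experience a DLT that resolves or stabilizes with appropriate medical management may continue treatment at the discretion of the Investigator". It adds that the Sponsor is consulted. No DLT type is carved out. The lead-in to Section 5 allows dosing to be suspended for up to one cycle "for any patient who experiences a protocol-defined DLT", and continues: "Resumption of dosing with ADCT-502 after any suspension, even when longer than 21 days, is at the discretion of the Investigator", again in consultation with the Sponsor.

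**The stop orders.** Section 5.3 says of liver injury: "Permanently discontinue ADCT-502 for any case meeting Hy's Law criteria". For a Grade 3 hypersensitivity or infusion-related reaction it says: "Permanently discontinue ADCT-502 unless AE resolves within 24 hours after onset (with or without clinical management"). For Grade 4 reactions the order has no exception. Section 5.2 gives the same unconditional order for Grade 4 febrile neutropenia.

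**The linking text.** Section 5.1 first sends the reader to 5.2, 5.3 and 5.4 for specific toxicities, then introduces its own table: "For management of events not specified in these sections, the following may serve as a guidance to investigators". That softening covers only events the later sections do not address.

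**The concern.** All three events are DLTs under Section 4.6.2. If one of them resolves or stabilises, 4.6.2 permits further dosing while the management table orders a permanent stop. Nothing in the protocol tells the site or the Sponsor's medical staff which instruction prevails.

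The stake is the individual patient: re-exposure after possible drug-induced liver injury, a severe or life-threatening reaction, or Grade 4 febrile neutropenia, in a first-in-human study of a DNA cross-linking conjugate. Two sites consulting the Sponsor in good faith could handle identical cases differently, and the one that resumed would have followed 4.6.2 while breaching 5.2 or 5.3.

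**Working it through.** The plan states no figure on this point and no arithmetic beyond a count applies. The check matches each DLT row in Section 4.6.2 (7 hematologic + 3 non-hematologic = 10) to its management row, then looks for a rule of precedence.

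**Step 1. Rows side by side**

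| DLT row(s) in 4.6.2 | Rows | Management in 5.2–5.4 | Conflict with 4.6.2 |
|---|---|---|---|
| Hy's Law case | 1 | Permanent stop, every case (5.3) | Whole row |
| Hypersensitivity/infusion-related reaction | 1 | Permanent stop at Grade 4, and at Grade 3 unless resolved within 24 hours (5.3) | In part, but nearly all |
| Febrile neutropenia or neutropenic infection | 1 | Febrile neutropenia: permanent stop at Grade 4; Grade 3 may resume one level lower (5.2) | In part, Grade 4 only |
| Other non-hematologic, Grade 3–4 | 1 | Stop for confirmed CHF or confirmed LVEF <40% (5.4) | Conditional |
| Neutropenia (1), thrombocytopenia (3), anemia (2) | 6 | Hold, then resume if recovery is timely (5.2) | None when recovery is timely |

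Total: 3 + 1 + 6 = 10.

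**Step 2. Borderline cases**

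- Section 4.6.2 says a Grade 3 "infusion-related reaction that resolves within 24 hours after onset with appropriate clinical management does not qualify as a DLT". A Grade 3 reaction that clears unaided within 24 hours is therefore literally still a DLT, but Section 5.3 does not order a stop for it. It is no conflict, and it is why the row counts as partial.
- Neutropenic infection has no row of its own in Section 5.2 and is not counted.
- The Grade 4 row of Section 5.1 also says to stop for good, but it sits under the guidance wording and is not counted.
- For the cardiac row, the first scheduled on-treatment ECHO or MUGA comes after Cycle 1 (Schedule of Events, footnote 12). Within the 21-day DLT window the issue is therefore mainly symptomatic CHF.

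**Step 3. Is precedence stated?** Four places could have settled it:

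- Section 5.1 routes specific toxicities to 5.2–5.4 but does not rank those sections against 4.6.2.
- Section 7 lists a delay beyond 21 days as a reason for withdrawal, with a Sponsor-approved exception for potential benefit. It does not address event-specific stops.
- The Amendment 2 summary explains why resumption after more than 21 days was extended to DLTs. It does not mention the stop orders.
- Section 4.6.1 gives the DESC ongoing safety review but no rule for this case.

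Statements of precedence found: 0.

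**Step 4. Can precedence be inferred?** The natural inference is that a specific order beats a general permission. The protocol's own usage undercuts it. Many rows in 5.2 and 5.3 say "permanently discontinue ADCT-502" when recovery takes longer than 21 days from the missed dose. For exactly those cases Section 5 allows resumption, Section 7 allows an exception, and the Amendment 2 summary confirms this was intended for DLTs. So essentially the same instruction, in the same tables, yields to general discretion in one class of case. Nothing says it is absolute in the other.

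**The case against.** The strongest defence is that there is no contradiction. Section 4.6.2 is permissive: it says only that a DLT does not automatically end treatment. Sections 5.2 and 5.3 then say when it must end. Both can be obeyed by stopping, and Section 5.1 points to those sections for specific toxicities. This joint reading is plausible, and it may be what the authors meant. It fails as a safe inference only because of the 21-day cases in Step 4.

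A second defence is that 5.2–5.4 are headed as guidelines. They are, but the expressly advisory phrase in 5.1 is confined to other events. If the stop orders were meant as advice, that too would need saying.

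A third defence is that Sponsor consultation and DESC review protect patients. These are real safeguards, so resumption is never the Investigator's decision alone. They do not supply a rule.

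Three stronger readings are tempting and should not be adopted:

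- *Section 5's lead-in is a second, separate conflict.* It speaks of resuming after a suspension, and a permanent stop is arguably not a suspension. It reinforces 4.6.2 and no more.
- *The cardiac rules conflict just as badly.* Section 5.4 and Table 3 already follow a hold, repeat and stop-if-confirmed path, and the resumption sentence in 5.4 fits the unconfirmed branch. What remains is that 5.4 does not say so, and mentions Grade 3 or higher dysfunction as an example of a hold that may be followed by resumption.
- *Dose finding is compromised.* A DLT counts in the mCRM whether or not the patient is later re-dosed, so the MTD and stopping rules are untouched.

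**Conclusion.** The point holds as a gap in precedence with a patient-safety consequence. Section 4.6.2 permits continuation after any DLT that settles. Sections 5.2–5.3 order a permanent stop for three kinds of DLT. The documents neither state which governs nor apply one ordering consistently.

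The scope is three of ten DLT rows, one wholly and two in part, with a fourth conditional through Section 5.4. These counts show breadth, not frequency; no expected event rates are given, so none is claimed. The conclusion assumes that 4.6.2 is read as written, without an unstated exception.

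The clarification should be made. SAP Section 3.3 records that the trial ended early and Part 2 was not performed, and SAP Section 4.8.1 only lists DLTs. No analysis changes, and the practical value now lies in correcting the text before it is reused.

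**What to change.** Add a named exception to the continuation sentence in Section 4.6.2 and to the resumption sentence in the Section 5 lead-in, for example:

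> except that ADCT-502 must be permanently discontinued for any Hy's Law case, a Grade 4 hypersensitivity/infusion-related reaction or a Grade 3 reaction not resolved within 24 hours, Grade 4 febrile neutropenia, confirmed CHF, or LVEF <40% confirmed on repeat; the discretion to resume after a delay longer than 21 days is otherwise unchanged.

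Naming the events matters. A blanket exception for whatever 5.2–5.4 say would cancel the deliberate discretion beyond 21 days, because those tables also order a stop for slow recovery. An exception limited to stops that apply regardless of recovery would miss the Grade 3 reaction, which turns on resolution within 24 hours, and LVEF <40%, which turns on the repeat measurement.

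Optionally, state in Section 5.4 that resumption applies only where CHF or LVEF <40% was not confirmed.

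The cost is one clause in two sentences and, if taken up, one qualifier in 5.4, by amendment or clarification letter. The downside is slightly less Investigator discretion, only for events where the protocol already calls for a stop.

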## 5 Management of Toxicity Including Dose Delays and Modifications

The Investigator may suspend ADCT-502 dosing for up to 1 cycle (i.e., 21 days of the default dosing schedule) for any patient who experiences a protocol-defined DLT. At the discretion of the Investigator, the dose may also be delayed for up to 21 days for any other toxicity of any grade.

Resumption of dosing with ADCT-502 after any suspension, even when longer than 21 days, is at the discretion of the Investigator, in consultation with the Sponsor, on assessment of the patient's clinical condition and whether or not the patient is deriving potential clinical benefit from treatment with ADCT-502.

## 5.1 ADCT-502 General Dose Modification Guidelines

Guidelines for management of specific toxicities are detailed in [Sections 5.2, 5.3, and 5.4](#). For management of events not specified in these sections, the following may serve as a guidance to investigators:

AE Grade	ADCT-502 Management Guideline
1	No dose adjustment is required.
2	
First Occurrence:
 
Consider holding ADCT-502 until improvement to <math>\leq</math> Grade 1 or Baseline. Up to 1 dose of ADCT-502 may be skipped to permit improvement. If improvement to <math>\leq</math> Grade 1 or Baseline occurs within 21 days from the last scheduled (but missed) ADCT-502 dose, continue ADCT-502 at the original assigned dose level in subsequent treatment cycles.
 
If improvement to <math>\leq</math> Grade 1 or Baseline does not occur within 21 days from the last scheduled (but missed) ADCT-502 dose, permanently discontinue ADCT-502.
 
Second Occurrence:
 
Hold ADCT-502 until improvement to <math>\leq</math> Grade 1 or Baseline. Up to 1 dose of ADCT-502 may be skipped to permit resolution. If improvement to <math>\leq</math> Grade 1 or Baseline occurs within 21 days from the last scheduled (but missed) ADCT-502 dose, continue ADCT-502 at 1 dose level below the original assigned dose in subsequent treatment cycles. If improvement to <math>\leq</math> Grade 1 or Baseline does not occur within 21 days from the last scheduled (but missed) ADCT-502 dose, permanently discontinue ADCT-502.
 
Third Occurrence:
 
Permanently discontinue ADCT-502.

3	
First Occurrence:
 
Hold ADCT-502 until improvement to <math>\leq</math> Grade 1 or Baseline. Up to 1 dose of ADCT-502 may be skipped to permit improvement, then continue ADCT-502 at 1 dose level below the original assigned dose in subsequent treatment cycles.
 
Second Occurrence:
 
Permanently discontinue ADCT-502.

4	Permanently discontinue ADCT-502.

## 5.2 Guidelines for Dose Modification: Hematologic Toxicities

Adverse Event	Grade	ADCT-502 Management Guideline
Febrile neutropenia	3	Hold ADCT-502 until the patient recovers. Up to 1 dose of ADCT-502 may be skipped to permit improvement. Consider use of granulocyte colony stimulating factor (G-CSF) as per institutional guidelines or as per ASCO guidelines. G-CSF prior to ADCT-502 is not allowed unless approved by sponsor.

Adverse Event	Grade	ADCT-502 Management Guideline
		
First Occurrence:
 
If patient recovers from febrile neutropenia prior to next scheduled dose or within 21 days from last scheduled (but missed) ADCT-502 dose, then continue ADCT-502 at 1 dose level below the original assigned dose in subsequent treatment cycles. If the patient does not recover within 21 days from the last scheduled (but missed) ADCT-502 dose, permanently discontinue ADCT-502.
 
Second Occurrence:
 
Permanently discontinue ADCT-502 if febrile neutropenia recurs despite ADCT-502 dose reduction.

Febrile neutropenia	4	Permanently discontinue ADCT-502.
Thrombocytopenia with significant bleeding or platelet transfusion required as per PI assessment	3	
Hold ADCT-502 until bleeding has stopped and improvement has occurred to <math>\leq</math> Grade 1. Up to 1 dose of ADCT-502 may be skipped to permit improvement.
 
First Occurrence:
 
Upon improvement to <math>\leq</math> Grade 1 within 21 days from last scheduled (but missed) ADCT-502 dose, continue ADCT-502 at 1 dose level below the original assigned dose in subsequent treatment cycles.
 
If improvement to CTCAE <math>\leq</math> Grade 1 does not occur within 21 days from the last scheduled (but missed) ADCT-502 dose, permanently discontinue ADCT-502.
 
Second Occurrence:
 
Upon improvement to <math>\leq</math> Grade 1 within 21 days from last scheduled (but missed) ADCT-502 dose, continue ADCT-502 at 2 dose levels below the original assigned dose in subsequent treatment cycles.
 
If improvement to <math>\leq</math> Grade 1 does not occur within 21 days from the last scheduled (but missed) ADCT-502 dose, permanently discontinue ADCT-502.
 
Third Occurrence:
 
Permanently discontinue ADCT-502.

Thrombocytopenia (regardless of whether significant bleeding is present or not)	4	
Hold ADCT-502 until bleeding has stopped and improvement has occurred to <math>\leq</math> Grade 1. Up to 1 dose of ADCT-502 may be skipped to permit improvement.
 
First Occurrence:
 
Upon improvement to <math>\leq</math> Grade 1 within 21 days from last scheduled (but missed) ADCT-502 dose, continue ADCT-502 at 1 dose level below the original assigned dose in subsequent treatment cycles.
 
If improvement to CTCAE <math>\leq</math> Grade 1 does not occur within 21 days from the last scheduled (but missed) ADCT-502 dose, permanently discontinue

Adverse Event	Grade	ADCT-502 Management Guideline
		
ADCT-502.
 
Second Occurrence:
 
Upon improvement to <math>\leq</math> Grade 1 within 21 days from last scheduled (but missed) ADCT-502 dose, continue ADCT-502 at 2 dose levels below the original assigned dose in subsequent treatment cycles.
 
If improvement to <math>\leq</math> Grade 1 does not occur within 21 days from the last scheduled (but missed) ADCT-502 dose, permanently discontinue ADCT-502.
 
Third Occurrence:
 
Permanently discontinue ADCT-502.

Neutropenia or thrombocytopenia (in the absence of bleeding)	3	
Hold ADCT-502 until improvement to <math>\leq</math> Grade 1. Up to 1 dose of ADCT-502 may be skipped to permit improvement. Consider use of G-CSF as per institutional guidelines or as per ASCO guidelines. G-CSF prior to ADCT-502 is not allowed unless approved by sponsor.
 
First Occurrence:
 
If improvement to <math>\leq</math> Grade 1 within 21 days from last scheduled (but missed) ADCT-502 dose, then continue ADCT-502 at original assigned dose in subsequent treatment cycles.
 
If improvement to <math>\leq</math> Grade 1 does not occur within 21 days from the last scheduled (but missed) ADCT-502 dose, permanently discontinue ADCT-502.
 
Second Occurrence:
 
If improvement to <math>\leq</math> Grade 1 within 21 days from last scheduled (but missed) ADCT-502 dose, then continue ADCT-502 at 1 dose level below the original assigned dose in subsequent treatment cycles.
 
If improvement to <math>\leq</math> Grade 1 does not occur within 21 days from the last scheduled (but missed) ADCT-502 dose, permanently discontinue ADCT-502.
 
Third Occurrence:
 
Permanently discontinue ADCT-502

Neutropenia	4	
Hold ADCT-502 until improvement to <math>\leq</math> Grade 1. Up to 1 dose of ADCT-502 may be skipped to permit improvement. Consider use of G-CSF as per institutional guidelines or as per ASCO guidelines. G-CSF prior to ADCT-502 is not allowed unless approved by sponsor.
 
First Occurrence:
 
If improvement to <math>\leq</math> Grade 1 within 21 days from last scheduled (but missed) ADCT-502 dose, then continue ADCT-502 at original assigned dose in subsequent treatment cycles. If improvement to <math>\leq</math> Grade 1 does not occur within 21 days from the last scheduled (but missed)

Adverse Event	Grade	ADCT-502 Management Guideline
		
ADCT-502 dose, permanently discontinue ADCT-502.
 
Second Occurrence:
 
If improvement to <math>\leq</math> Grade 1 within 21 days from last scheduled (but missed) ADCT-502 dose, then continue ADCT-502 at 1 dose level below the original assigned dose in subsequent treatment cycles.
 
If improvement to <math>\leq</math> Grade 1 does not occur within 21 days from the last scheduled (but missed) ADCT-502 dose, permanently discontinue ADCT-502.
 
Third Occurrence:
 
Permanently discontinue ADCT-502.

Anemia	3	
Hold ADCT-502 until improvement to <math>\leq</math> Grade 1 or Baseline.
 
Up to 1 dose of ADCT-502 may be skipped to permit improvement.
 
Consider use of erythropoietin (EPO) as per institutional guidelines.
 
First Occurrence:
 
If improvement to <math>\leq</math> Grade 1 or Baseline prior to next scheduled dose, continue ADCT-502 at the original assigned dose at the next scheduled treatment cycle. If improvement to <math>\leq</math> Grade 1 or Baseline within 21 days from last scheduled (but missed) ADCT-502 dose, then continue ADCT-502 at 1 dose level below the original assigned dose in subsequent treatment cycles. If improvement to <math>\leq</math> Grade 1 or Baseline does not occur within 21 days from the last scheduled (but missed) ADCT-502 dose, permanently discontinue ADCT-502.
 
Second Occurrence:
 
If improvement to <math>\leq</math> Grade 1 or Baseline within 21 days from last scheduled (but missed) ADCT-502 dose, then continue ADCT-502 at 2 dose level below the original assigned dose in subsequent treatment cycles. If improvement to <math>\leq</math> Grade 1 or Baseline does not occur within 21 days from the last scheduled (but missed) ADCT-502 dose, permanently discontinue ADCT-502.
 
Third Occurrence:
 
Permanently discontinue ADCT-502.

Anemia	4	
Hold ADCT-502 until improvement to <math>\leq</math> Grade 1 or Baseline.
 
Up to 1 dose of ADCT-502 may be skipped to permit improvement.
 
Consider use of EPO as per institutional guidelines.
 
First Occurrence:
 
If improvement to <math>\leq</math> Grade 1 or Baseline within 21 days from last scheduled (but missed) ADCT-502 dose, then continue ADCT-502 at 1 dose level below the original assigned dose in subsequent treatment cycles. If improvement to <math>\leq</math> Grade 1 or Baseline does not occur within 21 days from the last scheduled (but missed) ADCT-502 dose,

Adverse Event	Grade	ADCT-502 Management Guideline
		
permanently discontinue ADCT-502.
 
Second Occurrence:
 
If improvement to <math>\leq</math> Grade 1 or Baseline within 21 days from last scheduled (but missed) ADCT-502 dose, then continue ADCT-502 at 2 dose level below the original assigned dose in subsequent treatment cycles. If improvement to <math>\leq</math> Grade 1 or Baseline does not occur within 21 days from the last scheduled (but missed) ADCT-502 dose, permanently discontinue ADCT-502.
 
Third Occurrence:
 
Permanently discontinue ADCT-502.

